19.3 Appendix-C Prior and Concomitant Medication Start/Stop Date Imputation

Imputation Rules for Partial Dates (D = day, M = month, Y = year)

Parameter	Missing	Additional Conditions	Imputation
Start date for con meds	D only	M and Y same as M and Y of investigational product administration	Date of investigational product administration
		M and/or Y not same as date investigational product administration	First day of month
	M and D	Y same as Y of investigational product administration	Date of investigational product administration
		Y not same as Y of investigational product administration	Use Jan 01 of Y
	M, D, and Y	None - date completely missing	Day prior to date investigational product administration
Stop date for con meds	D only	M and Y same as M and Y of investigational product administration	Date of investigational product administration
		M and/or Y not same as date of investigational product administration	Last day of month
	M and D	Y same as Y of investigational product administration	Date of investigational product administration
		Y not same as Y of investigational product administration	Use Dec 31
	M, D, and Y	None - date completely missing and NOT ongoing	Date of investigational product administration

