13.6.6. Prior and Concomitant Medications

Medications will be recorded at each study visit during the study and will be coded using World Health Organization-Drug dictionary (WHO-DD) September 2015, or later.

All medications and supplements taken within 60 days prior to informed consent through the duration of the study will be recorded, as well as all medications used to treat PD regardless of timing. Those medications taken prior to the first dose of IP will be denoted “Prior”. Those medications taken prior to the first dose of IP and continuing beyond the initiation of the IP or those medications started at the same time or after the initiation of the IP will be denoted “Concomitant”.

Medications will be presented according to whether they are “Prior” or “Concomitant” as defined above. If medication dates are incomplete and it is not clear whether the medication was concomitant, it will be assumed to be concomitant.

Details of prior and concomitant medications will be listed by participant, start date, and verbatim term.

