13.8 Prior and Concomitant Medications

The following analyses will use the Safety Set.

All medications taken and procedures undergone during the study will be recorded.

Medications will be presented according to whether they are being taken prior to and/or during the study (concomitant). Prior medications are defined as those taken prior to the initiation of the start of the investigational product, and that ended prior to the IP. Concomitant medications are defined as those with a start date on or after the first dose of investigational product or those with a start date before the first dose of investigational product that is ongoing or with a stop date on or after the first dose of investigational product.

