19.4 Appendix-D Adverse Event Start/Stop Date Imputation

[figure not shown]
Parameter	Missing	Additional Conditions	Imputation
Start date for AEs	D	M and Y same as M and Y of investigational product administration	Date of investigational product administration
		M and/or Y not same as date investigational product administration	First day of month
	D and M	Y same as Y of investigational product administration	Date of investigational product administration
		Y prior to Y of investigational product administration but same as Y of screening date	Date of screening date
	D, M, Y	None - date completely missing	Date of investigational product
Stop date for AEs	D	M and Y same as M and Y of investigational product administration	Date of investigational product administration
		M and/or Y not same as date of investigational product administration	Use last day of month
	D and M	Y same as Y of investigational product administration	Date of investigational product
		Y not same as Y of investigational product administration	Use Dec 31
	D, M, Y	None - date completely missing	No imputation, but assume ongoing

[figure not shown]
Note: In all cases, if an estimated start date is after a complete stop date, use the first day of the stop date month. Similarly, if the estimated stop date is before a complete or imputed start date, use the last day of the start day month.

[figure not shown]

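### SAP Appendix C can start a medication on the dosing day although it is known to have stopped earlier, so it is tabulated as concomitant; its stop rule can also place a stop before the start

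*SAP*

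**What the plan says.** SAP Appendix C replaces a partial medication start date with the date of investigational product (IP) administration in two situations:

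- the day is missing and "M and Y same as M and Y of investigational product administration";
- day and month are missing and "Y same as Y of investigational product administration".

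A wholly missing start goes to the day before IP. Partial stop dates go to the IP date under the same two conditions, and so does a wholly missing stop under the condition "None - date completely missing and NOT ongoing". Where month or year does not match, partial stops go to the last day of the month or 31 December. No start row refers to the stop date, and no stop row refers to the start date.

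SAP 13.8 then classifies: "Concomitant medications are defined as those with a start date on or after the first dose of investigational product". A drug started earlier is also concomitant if it is "ongoing or with a stop date on or after the first dose of investigational product". Prior drugs are those taken before IP "and that ended prior to the IP".

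Protocol 13.6.6 sets the default: "If medication dates are incomplete and it is not clear whether the medication was concomitant, it will be assumed to be concomitant". SAP 6.1 declares only one change to that section, the addition of a summary table to the listing.

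A rule that repairs date order exists only under the adverse event table in SAP Appendix D: "if an estimated start date is after a complete stop date, use the first day of the stop date month". A second sentence there moves an estimated stop that falls before the start to the end of the start month.

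**The concern.** A complete stop date before first dose settles a drug's status: it was not taken during treatment. Appendix C ignores that information and can manufacture a start on the dosing day. By the start-date limb of SAP 13.8 the drug is then concomitant. By the prior definition in the same section it is prior. The SAP does not say which limb wins, and the protocol's default does not apply because nothing is unclear.

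At stake are the descriptive tables of prior and concomitant medications (SAP Tables 14.1.3 and 14.1.4, Parts A and B), along with any output that shows imputed dates. Protocol 9.2.1 says concomitant medications matter because of their possible effects on cognition. A concomitant table containing drugs that had already ended misdescribes the treated participants.

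**Working it through.** The documents give no figure to reproduce, so the check applies the rules literally. The IP date is read as the date of first dose, the anchor used in SAP 13.8. All calendar dates below are assumed.

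**1. Start known by year only.** First dose 1 June 2021, start 2021, complete stop 15 March 2021. The year matches, so the imputed start is 1 June 2021. From 15 March to 1 June is 16 + 30 + 31 + 1 = 78 days, so the start falls 78 days after the known stop. Start on or after first dose: concomitant. Ended before IP: prior as well.

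**2. Start day missing.** First dose 20 June 2021, start June 2021, complete stop 10 June 2021. The imputed start is 20 June, 10 days after the stop, and the drug is again concomitant.

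**3. Which partial starts trigger it.** Take every start/stop pair in the 60 days before first dose, with the stop complete: 60 × 61 / 2 = 1,830 pairs. (The protocol counts its 60-day look-back from consent; counting from first dose is a simplification.)

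| Start date missing | Concomitant, first dose 5 June | Concomitant, first dose 20 June |
|---|---|---|
| Day | 4 × 5 / 2 = 10 | 19 × 20 / 2 = 190 |
| Day and month | 1,830 | 1,830 |
| Day, month and year | 0 | 0 |

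With only the day missing, just the starts inside the dosing month count (4 or 19 earlier days). A wholly missing start never misclassifies, although 1,830 − 60 = 1,770 pairs still get a start after the stop; the 60 exceptions stop on the day before dosing. These counts show which rows fail. They are not frequencies, because recorded dates are not spread evenly over such a grid.

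**4. Stop dates.** First dose 1 June 2021, complete start 10 June 2021, stop June 2021. The imputed stop is 1 June, nine days before the start. The drug is still concomitant because its start follows first dose. A drug started before dosing and given a stop on the dosing day also stays concomitant, because its stop is on or after first dose.

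Over a 28-day course there are 27 × 28 / 2 = 378 pairs with start and stop both on Days 2 to 28. There are 60 × 27 = 1,620 pairs with a start in the 60 days before dosing and a stop on Days 2 to 28. All 378 and all 1,620 remain concomitant at every level of missingness. Among the 378, the imputed stop precedes the start in:

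- 25 × 26 / 2 = 325 (first dose 5 June) or 10 × 11 / 2 = 55 (first dose 20 June) when the stop day is missing;
- all 378 when more than the day is missing.

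**5. Size of one error.** With the planned numbers dosed, one participant is 1/11 = 9.1 percentage points of a Part A row and 1/22 = 4.5 of a Part B row.

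**The case against.** The best defence is that the Appendix D note is worded to apply throughout and could be read as covering medications. If so, none of the 1,830 pairs in step 3 would be concomitant. But the note is printed under the adverse event table, and Appendix C neither repeats it nor refers to it. Its first sentence also needs a complete stop date. With first dose 1 June 2021, start 2021 and stop March 2021, Appendix C gives a stop of 31 March and a start of 1 June. The second sentence of the note would then move the stop to 30 June, which is worse. Borrowing the note is therefore not a sufficient answer.

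A second defence is that the prior definition and the protocol default both point a careful programmer to the right class. That is fair. It means the SAP contradicts itself for these records, not that it settles on the wrong answer. A stated rule still yields concomitant.

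A third is that the trigger is narrow, and this largely stands. It needs a start in the dosing month or year, an incomplete start date and a stop known to precede dosing. Long-standing Parkinson's disease drugs started in an earlier year do not meet it, so collecting those drugs regardless of timing does not show that the error is likely. The day-missing branch needs start and stop both within the dosing month, a period mostly inside the four weeks of stable medication required by inclusion criterion 11. The year-only branch is not limited in that way: the stop in step 1 lies 78 days before dosing.

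Finally, the stop-date fault changes no visible table. This is correct.

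**Conclusion.** The point holds as a defect in a derivation rule. A drug known to have ended before first dose can be given a start after its stop and counted as concomitant. Separately, a drug started on treatment can be given a stop before its start. The first fault puts extra drugs in the concomitant table; the second affects imputed dates only. This rests on reading the IP date as first dose, which Appendix C leaves unstated although IP is taken on 14 or 28 days.

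The effect is confined to descriptive medication tables and imputed dates. How many records are affected cannot be estimated from the documents. The incidence of treatment-emergent adverse events, the primary endpoint, does not use these rules.

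Two stronger readings are tempting and not supported:

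- **That the stop rule hides overlap between a drug and the on-treatment assessments.** The drug stays in the concomitant table, and no visible table uses medication duration or overlap with visits.
- **That these tables are the only check on background treatment.** Stable medication is an entry criterion, changes are recorded at each visit, prohibited use is captured as a deviation (Protocol 9.2.2), deviations are listed, and Listing 16.2.4.3 shows medications by participant.

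**What to change.** In Appendix C:

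1. Anchor every rule to the date of first dose.
2. If the complete or imputed stop date is before first dose, classify the drug as prior and cap the imputed start at the stop date.
3. Never let an imputed stop precede the start. Where the known month or year matches that of first dose, use the last day of that month or 31 December, as the non-matching rows already do, capped at the participant's last study date.
4. Keep the assume-concomitant default only where the dates leave status unclear.

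The Appendix D note should not be copied over as it stands: it would set the start in step 1 to 1 March rather than cap it at 15 March, and it mishandles partial stops. A wholly missing stop marked as not ongoing should not be extended to study end, since that would override what the site recorded. It can stay at first dose, raised to the start date where the start is later.

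The cost is a few lines of SAP text and programming, with no new data. Some imputed stops will become later, so apparent durations lengthen, without changing the class of those drugs. If the database is already locked, SAP 6.0 requires the change and its justification to be described in the clinical study report.

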19.4 Appendix-D Adverse Event Start/Stop Date Imputation

[figure not shown]
Parameter	Missing	Additional Conditions	Imputation
Start date for AEs	D	M and Y same as M and Y of investigational product administration	Date of investigational product administration
		M and/or Y not same as date investigational product administration	First day of month
	D and M	Y same as Y of investigational product administration	Date of investigational product administration
		Y prior to Y of investigational product administration but same as Y of screening date	Date of screening date
	D, M, Y	None - date completely missing	Date of investigational product
Stop date for AEs	D	M and Y same as M and Y of investigational product administration	Date of investigational product administration
		M and/or Y not same as date of investigational product administration	Use last day of month
	D and M	Y same as Y of investigational product administration	Date of investigational product
		Y not same as Y of investigational product administration	Use Dec 31
	D, M, Y	None - date completely missing	No imputation, but assume ongoing

[figure not shown]
Note: In all cases, if an estimated start date is after a complete stop date, use the first day of the stop date month. Similarly, if the estimated stop date is before a complete or imputed start date, use the last day of the start day month.

[figure not shown]

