12.2. Adverse Events and Serious Adverse Events

12.2.1. Adverse Event Definition

An AE is any untoward medical occurrence in a patient or clinical investigation participant administered a pharmaceutical product and that does not necessarily have a causal relationship with this treatment. An AE can therefore be any unfavorable and unintended sign (including an abnormal laboratory finding), symptom or disease temporally associated with the use of a medicinal (investigational) product whether or not related to the medicinal (investigational) product. In clinical studies, an AE can include an undesirable medical condition occurring at any time, including baseline or washout periods, even if no study treatment has been administered.

A TEAE is defined as an AE with onset after the start of IP, or any worsening of a preexisting medical condition/AE with onset after the start of IP and throughout the study. The term IP includes any Sage IP, a comparator, or a placebo administered in a clinical study.

Laboratory abnormalities and changes from baseline in vital signs, and ECGs are considered AEs if they result in discontinuation or interruption of study treatment, require therapeutic medical intervention, meet protocol specific criteria (if applicable) or if the investigator considers them to be clinically significant. Any abnormalities that meet the criteria for a SAE should be reported in an expedited manner. Laboratory abnormalities and changes from baseline in vital signs and ECGs that are clearly attributable to another AE do not require discrete reporting (eg, electrolyte disturbances in the context of dehydration, chemistry, and hematologic disturbances in the context of sepsis).

All AEs that occur after any participant has signed the informed consent form (ICF) and throughout the duration of the study, whether or not they are related to the study, must be reported to Sage Therapeutics.

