9.0 Study Endpoints

9.1 Primary Endpoint

- Incidence of treatment-emergent adverse events (TEAEs)

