13.0 Statistical Methods

13.1 General Statistical Methodology

All analyses will use SAS version 9.4 or higher.

Unless otherwise noted, continuous variables will be summarized using the number of observations (n), mean, standard deviation (std), median, first quartile (Q1), third quartile (Q3), minimum, and maximum values. The minimum and maximum values will be displayed to the same level of precision as the raw data; the mean, median, Q1, and Q3 values to one additional decimal place and the std to two additional decimal places.

Categorical variables will be summarized using counts and percentages. Percentages will be rounded to one decimal place, except 100% will be displayed without any decimal places, and percentages will not be displayed for zero counts.

Any data points that are not within the expected range due to subjects not following task instructions to complete the tasks will be flagged as invalid by CANTAB EDC. These data points will be excluded from the analyses and reports.

All participants will be used in the analyses as per the analysis populations, using all non-missing data available. No imputation process will be used to estimate missing data.

For all safety, efficacy, and other analyses, where applicable, the baseline is defined as the last assessment prior to the first dose of study IP.

All summary tables will be reported separately for Part A and Part B studies.

For [REDACTED], the baseline is defined as the average assessments over 7 days immediately preceding Day 1.

Prior and concomitant medication start/stop date imputation and adverse event start/stop date imputation are described in Appendix 2 and Appendix 3, respectively.

AEs will be coded using Medical Dictionary for Regulatory Activities (MedDRA) version 23.0u. All TEAEs are defined as an AE with onset after the first dose of IP or any worsening of a preexisting medical condition/AE with onset after the start of IP and throughout the study.

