16.1 Adverse Events

TEAEs are defined as any AEs with an onset date on or after the date of the first dose of IP or any worsening of a preexisting medical condition/AE with onset after the start of IP and throughout the study. An AE leading to treatment discontinuation is defined as an AE with action taken of investigational product as Drug Withdrawn. AEs will be coded using the Medical Dictionary for Regulatory Activities MedDRA version 23.0u.

An overall summary of TEAEs, including the number of events, reported, the number and percentage of participants reporting at least one TEAE, the number and percentage of participants reporting at least one related TEAE, the number and percentage of participants by maximum severity, the number and percentage of participants discontinuing due to an adverse event, the number and percentage of participants with at least one serious adverse event, and the number and percentage of deaths will be presented.

A breakdown of the number and percentage of participants reporting each adverse event, categorized by System Organ Class (SOC) and preferred term (PT), will be presented. Note that counting will be by participant, not event, and participants are only counted once within each SOC and PT.

A further tabulation of these data, categorized by relationship (to SAGE-718), will be presented. Participants with multiple events within a particular body system or preferred term will be counted under the category of their drug-related event (related and not related) within SOC and PT. Relationship to SAGE-718 is categorized as related or not related.

A summary of events reported, categorized by severity, will also be provided. Participants with multiple events within a particular SOC and PT will be counted under the category of their most severe event in the following order: severe > moderate > mild within that SOC and PT.

A summary of adverse events leading to discontinuation of SAGE-718 will be provided, grouped by body system and preferred term.

All adverse events (including non-treatment-emergent events) recorded on the CRF will be listed.

Handling of missing AE start dates is defined in Appendix 3. Missing data for severity or relatedness to treatment will not be imputed.

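### Under SAP Appendix D, an AE recorded as ending in a month before first dose can count as treatment-emergent when its stop day and its start month are both missing

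*SAP*

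**What the plan says.** Four pieces of the SAP act together.

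- **Start-date rows, SAP 19.4 (Appendix D).** When day and month are missing and the condition is "Y same as Y of investigational product administration", the AE start becomes the date of IP administration. A wholly missing start gets the same date.
- **Stop-date rows, same table.** When only the day is missing and the condition is "M and/or Y not same as date of investigational product administration", the stop becomes the last day of the recorded month.
- **Note under the table.** Its first sentence reads: "if an estimated start date is after a complete stop date, use the first day of the stop date month". Its second reads: "if the estimated stop date is before a complete or imputed start date, use the last day of the start day month".
- **TEAE definition.** SAP 16.1 has "TEAEs are defined as any AEs with an onset date on or after the date of the first dose of IP", whereas SAP 13.1 has "All TEAEs are defined as an AE with onset after the first dose of IP". Protocol 13.6.1 agrees with SAP 13.1.

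SAP 9.1 makes the incidence of TEAEs the primary endpoint. Protocol 12.2.1 collects AEs from signed consent, so events from before dosing are in the database. Nothing in either document says that a recorded stop month before dosing rules out treatment-emergent status.

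**The concern.** Treating an uncertain onset as treatment-emergent is a reasonable convention in a safety study. Here, though, the onset is not uncertain in the way that matters. An event that ended in a calendar month before the month of first dose cannot have begun on or after first dose, whatever the missing day was.

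The note accepts this logic for a complete stop date and moves the imputed start back. It does not do so when the stop lacks only its day, although that day has no bearing on the question. A recorded month is then replaced by an imputed one, and the event enters the TEAE count. The count is the primary endpoint, and the Parts are planned at 11 and 22 participants.

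**Working it through.** There is no stated figure to reproduce; this is a date rule, so the check is to apply it literally. Two assumptions are needed: the date of IP administration in Appendix D means the first dose, and TEAE status follows SAP 16.1 (imputed onset on or after the first-dose date).

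**Worked example.** First dose 15 June 2021, start recorded as 2021 only, stop recorded as May 2021.

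1. Start row: the year matches dosing, so the start is 15 June.
2. Stop row: the month differs from dosing, so the stop is 31 May.
3. Note, first sentence: the stop is not complete, so the sentence does not apply.
4. Note, second sentence: the estimated stop (31 May) is before the imputed start (15 June), so the stop moves to 30 June.
5. SAP 16.1: an onset of 15 June falls on the first-dose date, so the event is a TEAE.

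The recorded stop month ended 15 days before dosing.

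**Neighbouring cases, same first dose.**

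| Recorded start | Recorded stop | Final dates under Appendix D | TEAE under SAP 16.1 |
|---|---|---|---|
| 2021 | May 2021 | 15 June to 30 June | Yes |
| 2021 | 28 May 2021 | 1 May to 28 May | No |
| wholly missing | May 2021 | 15 June to 30 June | Yes |
| wholly missing | 28 May 2021 | 1 May to 28 May | No |
| May 2021 | May 2021 | 1 May to 31 May | No |
| 2021 | June 2021 | 15 June to 15 June | Yes |

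Rows 1 and 3 are the fault. Rows 2 and 4 show that a complete stop in the same month is handled correctly. Row 5 shows that a known start month is also safe. In row 6 the stop falls in the dosing month, so the onset really is ambiguous and counting it is defensible.

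**Which step causes it.** TEAE status depends on onset alone. The start row sets the onset to the dosing date, and the first sentence of the note fails to correct it because it is limited to complete stops. The second sentence only settles the conflict in favour of the imputed start. Without it the stop would remain 31 May, but the start would still be 15 June and the event would still be counted.

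**When it can arise.** The rules were run for every first-dose date in 2021 and every pre-dose event lying within Day -21 to Day -1, assuming consent on Day -21, with the start cut to the year and the stop cut to month and year. For a first dose on day d of a month (d = 1 to 21), put m = 22 - d. Then m(m + 1)/2 start-stop pairs end in the previous month. Summed over d, this is 21 × 22 × 23 / 6 = 1,771 pairs for each calendar month.

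- Twelve months: 12 × 1,771 = 21,252 combinations with a stop month before the dosing month.
- February to December: 11 × 1,771 = 19,481, and all of these become TEAEs.
- January: the remaining 1,771 do not, because the start year is then the prior year and the screening-date row applies.

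This shows where the rule fails. It is not a probability, because it supposes that every date is partial.

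**Size.** One participant wrongly counted who has no other TEAE: 1/11 = 9.1 percentage points in Part A; 1/22 = 4.5 in Part B. A participant who has another TEAE leaves the overall incidence unchanged.

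**The case against.** **The case should almost never occur.** AEs are collected only from consent, screening assessments start at Day -21, Protocol 12.2.4 asks for onset and resolution date and time, and Protocol 14.1 provides for source data verification. If consent is on Day -21 in the example (25 May), an AE over in May must have begun between 25 and 31 May, so a start known only to the year ought to prompt a query. This stands, and it limits the severity. It does not make the rule right: imputation rules exist for the dates that queries fail to resolve.

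**The error is in the cautious direction.** It adds TEAEs and removes none, and all AEs are listed, including those that are not treatment-emergent. That is true. But caution is an answer to ambiguity, and here the recorded month removes it.

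**The TEAE definition is not settled.** Under SAP 13.1 and Protocol 13.6.1 onset must come after the first dose, and an onset imputed to the dosing date, with no time, is not clearly after it. This stands. The misclassification is definite only under SAP 16.1, so the wordings need to be reconciled.

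**Two stronger readings are tempting.** A reader might infer that the second sentence of the note creates the TEAE by overwriting the stop month. It does not, since the count would be the same without it. A reader might also infer that the sentence should give way to every partial stop date. That would do harm. Take a first dose on 20 June 2021, start recorded as July 2021 and stop as 2021. The table gives start 1 July and stop 20 June, and the second sentence correctly moves the stop to 31 July. If the imputed stop overruled the start instead, a known July onset would move to before dosing and a true TEAE would be lost. A complete start of 1 July with a stop of 2021 needs the same sentence, or its dates stay inverted.

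**Conclusion.** The point holds in a narrow form. If the AE start is known only to the dosing year or is wholly missing, and the stop has a recorded month and year before the month of first dose but no day, Appendix D with SAP 16.1 classes as treatment-emergent an event that the record shows was over before dosing. No other passage repairs this. The cause is the start-date row together with the limit to complete stops in the note's first sentence; the second sentence entrenches the result.

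The 9.1 and 4.5 points apply per affected participant with no other TEAE, at the planned 11 and 22 dosed. They are not an estimate of bias. The documents give no rate of partial dates, so they do not support an inference that the primary endpoint is materially distorted. The severity is low: a rare fault, upward in direction and cheap to remove.

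**What to change.** Change the note in Appendix D and align the definitions.

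1. **Extend the first sentence.** It should apply to a complete stop date, as now, and also to a stop date whose recorded month and year precede the month of first dose. In the added case, a start with day and month missing, or missing altogether, moves to the first day of the stop month (or to the consent date if later). The recorded stop month is kept, and the AE is not treatment-emergent.
2. **Leave the second sentence as it is for all other cases**, including stops known only to the year and starts that are complete or known to the month.
3. **Reconcile the onset wording** in SAP 13.1 and Protocol 13.6.1 with SAP 16.1, and state how an onset imputed to the dosing date is classed.

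Extending the first sentence, tested without the consent-date limit, changes the example to 1 May to 31 May 2021, not a TEAE. With that limit and consent on 25 May, the start would be 25 May, with the same classification. The tested cases with a complete stop, a stop in the dosing month or a stop known only to the year do not change. The cost is one sentence in Appendix D, one line of derivation code and a wording correction to the TEAE definition.
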